10.4 IND Safety Reports to the FDA (Refer to 21 CFR 312.32)

The Sponsor will notify the FDA of any unexpected fatal or life-threatening suspected adverse reactions as soon as possible but no later than 7 calendar days of initial receipt of the information using the MedWatch Form 3500a.

The Sponsor is also responsible for reporting any:

- suspected adverse reaction that is both serious and unexpected
- any findings from clinical, epidemiological, or pooled analysis of multiple studies or any findings from animal or in vitro testing that suggest a significant risk in humans exposed to the drug
- clinically important increase in the rate of a serious suspected adverse reaction over that listed in the protocol or investigator brochure

to the FDA and to all investigators no later than 15 calendar days after determining that the information qualifies for reporting using the MedWatch Form 3500a. If FDA requests any additional data or information, the sponsor must submit it to the FDA as soon as possible, but no later than 15 calendar days after receiving the request.

10.4.1 FDA Annual Reports (Refer to [21 CFR 312.33](#))

The study Sponsor will submit a brief report annually of the progress of the trial within 60 days of the anniversary date that the IND went into effect as indicated in 21CFR 312.33, and any associated FDA correspondences regarding the IND annual report.

Responsibility of Participating Sites	Responsibility of Montefiore-Einstein

 • Participating sites are responsible for reporting all events to their local IRB per local guidelines • Participating sites are responsible for reporting all SAEs (section 10.3) to the Montefiore-Einstein PI via fax or email within 24 hours of learning of the event. 	
 • The Montefiore-Einstein Research Staff is responsible for submitting all reportable events to the IRB as specified in section 10.2 • The Montefiore-Einstein PI will be responsible for reporting all drug related serious adverse events to the FDA (section 10.4) and events noted in section 10.3 to study supporters • The Montefiore-Einstein PI is responsible for informing all participating sites about unanticipated problems and fatalities within 30 days of receiving the stamped reportable events form from the IRB.

11 RESPONSE CRITERIA

MDS Response Criteria: Modified International MDS Working Group (IWG) Criteria for Measurement of Response/Treatment Effect in MDS (20) will be used to assess response.

Complete Remission (CR)

Bone marrow evaluation (>4 weeks): Bone marrow showing \leq 5% myeloblasts with normal maturation of all cell lines. When erythroid precursors constitute < 50% of bone marrow nucleated cells, the percent of blasts is based on all nucleated cells; when there are > 50% erythroid cells, the percent blasts should be based on the non-erythroid cells. This response should last for at least 4 weeks. Dysplasia if present will be noted.

Peripheral Blood Counts (Absolute values must last >4 weeks)

- o Hemoglobin greater than 11 g/dL (untransfused, patient not on erythropoietin).
- o Neutrophils 1000/mm³ or more (not on a myeloid growth factor)
- o Platelets 100 000/mm³ or more (not on a thrombopoietic agent)
- o Blasts – 0%
- o Hematologic improvement should be obtained.

Marrow CR: Bone marrow: < 5% myeloblasts and decrease by > 50% over pretreatment marrow. Peripheral blood: if hematologic improvement occurs, it will be noted in addition to marrow CR

Partial Remission (PR)

All of the CR criteria (if abnormal prior to treatment), except

- o Bone marrow evaluation: Blasts decreased by 50% over pretreatment, b

Stable Disease

Failure to achieve at least a PR, but with no evidence of progression for >8 weeks.

Failure

Death during treatment or disease progression characterized by worsening of cytopenias, increase in the percent of bone marrow blasts, or progression to an MDS FAB subtype more advanced than pretreatment.

Relapse (following a CR or PR)

One or more of the following:

- o Return to pretreatment bone marrow blast percentage.
- o Decrement of > 50% from maximum remission response levels in neutrophils or platelets.
- o RBC transfusion dependence (> 2 units RBC transfusions over an 8 week period) or a reduction in hemoglobin concentration by >1.5 g/dL in the absence of acute infection, gastrointestinal bleeding, hemolysis, treatment hiatus etc.

6. Disease Progression

A 50 % increase in blasts, depending on baseline blastpercent, if confirmed by subsequent BM examination (Fig 5).

- o For patients with < 5% blasts: increase to > 10% blasts
- o For patients with 5% to 10% blasts: > 50% increase to > 10% blasts
- o For patients with 10% to 20% blasts: > 50% increase to 20% blasts
- o For patients with 20% to 30% blasts: > 50% increase to 30% blasts

Any of the following:

At least 50% decrement from maximum remission/response in granulocytes or platelets

Reduction in Hgb by 2 g/dL

Transfusion dependence

7. Disease Transformation

Transformation to AML (> 30% blasts).

Cytogenetic Response

Requires 20 analyzable metaphases when using conventional techniques. Analysis of data will require 20 metaphases before and after treatment. Fluorescent *in situ* hybridization (FISH) may be used as a supplement to follow a specifically defined cytogenetic abnormality, but it is not a substitute for conventional cytogenetic studies.

Cytogenetic response is defined as follows:

Complete response: Restoration of a normal karyotype in patients with a documented pre-existing clonal (>2 metaphases abnormal) chromosome abnormalities.

Partial response: > 50% reduction in the percentage of bone marrow metaphases with only clonal abnormality.

Hematologic Improvement

Improvements must last >8 consecutive weeks.

1. Erythroid Response

Hgb increase by 1.5 g/dL if not transfusion dependent Relevant reduction of units of RBC transfusions by an absolute number of at least 4 RBC transfusions/8 wk compared with the pretreatment transfusion number in the previous 8 wk. Only RBC transfusions given for a Hgb of 9.0 g/dL pretreatment will count in the RBC transfusion response evaluation

2. Platelet Response

For patients with a pretreatment count < 100,000/mm³, an absolute increase of > 30,000/mm³ (for patients with pretreatment counts >20,000).

For patients with pretreatment counts < 20,000, an increase to absolute count above 20,000 by at least 100% increase will be considered as response.

†;for platelet transfusion-dependent patients, stabilization of platelet counts and platelet transfusion independence.

3. Neutrophil Response

At least 100% increase and an absolute increase $> 0.5 \times 10^9/L$

4. Progression/Relapse Following Erythroid Hematologic Improvement

At least 1 of the following:

At least 50% decrement from maximum response levels in granulocytes or platelets

Reduction in Hgb by 1.5 g/dL

Transfusion dependence

Duration of Response

Time to disease progression (as per Bone Marrow Responses above) or progression/relapse following hematologic improvement (as per Hematologic Improvement above).

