Ineffective erythropoiesis remains the hallmark of myelodysplastic syndromes (MDS) for which few treatments offer sustained erythropoietic improvement (13). Lenalidomide (CC-5013; REVLIMID[®]) is an oral 4-amino glutarimide derivative of thalidomide that lacks the neurological toxicities of the parent compound. In a safety and efficacy study (MDS-001) investigating erythroid response to CC-5013 (lenalidomide) monotherapy in 43 patients with MDS, CC-5013 (lenalidomide) yielded a high frequency of major erythroid response (MER) in patients that had either failed prior treatment with erythropoietin or had high endogenous levels and high transfusion burden (14). Patients received treatment with one of three CC-5013 (lenalidomide) dose schedules, 25 or 10 mg daily, or 10 mg/day x 21 days every 4 weeks. Neutropenia (67%) and thrombocytopenia (57%) > grade 3 NCI-CTC version 2.0 were dose limiting, necessitating treatment interruption and dose-reduction in 25 (61%) patients. Other adverse effects were infrequent and of mild to moderate severity including pruritus, fatigue, diarrhea, edema, thyroid dysfunction and joint discomfort. Among the 36 patients completing more than one cycle of treatment, 24 (67%) experienced an erythroid response according to International Working Group (IWG) criteria. MER defined by sustained transfusion-independence (> 8 weeks) or a rise in hemoglobin >2 g/dl was achieved in 21 patients and 3 patients experienced a >50% reduction in red blood cell

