(RBC) transfusions. Response rate was highest among evaluable patients with a chromosome 5q31.1 deletion (91%) compared to those with a normal karyotype (68%) or other chromosome abnormality (17%) [$P=0.009$], and response rate was higher in patients with lower (Low-/Intermediate-1) International Prognostic Scoring System (IPSS) risk categories (72% vs. 25%) [$P=0.098$] (15). Eleven of 17 (65%) patients with karyotypic abnormalities had a 50% or greater reduction in abnormal metaphases, including ten (57%) complete cytogenetic remissions. After a median follow-up of 109 weeks in November 2004, median duration of transfusion-independence had not been reached (81+; range, 19 to >128 weeks) with a median sustained hemoglobin (Hgb) of 13.4 g/dL (range, 11.5-15.8 g/dL) and median Hgb rise of 5.6 g/dL. The results of this study indicate that CC-5013 (lenalidomide) has significant and sustained erythropoietic and cytogenetic remitting activity in patients with Low/Intermediate-1 IPSS risk MDS that have failed or are unlikely to benefit from conventional cytokine therapy. Two phase II multicenter trials were completed in the past year, evaluating the frequency of MER to lenalidomide in patients with transfusion-dependent Low/Int-1 risk MDS with (MDS-003; N=148) or without a chromosome 5q31.1 deletion (MDS-002; N=215). Intent-to-treat analysis of the data confirm the high response rate in patients with del 5q31.1 (MER 66%, MER + Minor erythroid response 75%, cytogenetic response 70%) compared to a MER rate of 27% and Minor + MER rate of 44% in the MDS-002 results (15, 16). Grade 3 or greater neutropenia or thrombocytopenia were the principal reasons for treatment interruption and dose-reduction.

3.5 Rationale for combining lenalidomide and eltrombopag:

The rationale for combination is based on the following:

1. A major reason why lenalidomide cannot be used in MDS is because of the occurrence of thrombocytopenia. The use of EP will potentially raise platelet counts in these patients.
2. Thrombocytopenia in the first 2 months after Len therapy predicts the subsequent response to lenalidomide treatment in patients with low risk MDS (17) Thus raising platelet counts to enable continuation of lenalidomide therapy is important in these patients.

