4.1.2 Secondary Objectives

- To compare the time to hematologic improvement
- To evaluate the duration of hematologic improvement
- To evaluate the effect of combination treatment on platelet counts, platelet transfusions and bleeding events.
- To evaluate the frequency of bone marrow response (CR+PR) and cytogenetic response.
- To evaluate the relationship between mutations in bone marrow stem cells and response
- To evaluate the relationship between various stem and progenitor alterations and response

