14.2 Sample size and power considerations

The primary outcome is major erythroid response. A maximum of 52 patients will be enrolled into the study. An early stopping rule for lack of efficacy will be implemented as follows based on Simon's optimal two-stage design. After the first 25 patients have been enrolled and evaluated for response, the trial will be terminated early if fewer than 7 patients respond to treatment. If 7 or more responses are observed, the trial will continue until a total of 52 patients have been evaluated. At the end of the trial, the treatment will be considered efficacious and worthy of further study if 17 or more patients respond out of 52 patients.

The target response rate is assumed to be 40%. (Conservative estimate) A response rate less than 25% is considered to be clinically unimportant(21). Under these assumptions, the design specified above has the following operating characteristics. The probability of accepting the treatment for further study if the response rate is unacceptably low

(<25%) is at most 10%. In contrast, there is a 80% probability of accepting the treatment for further study if the response rate is at least 40%. The expected sample size is 32.4 subjects. It is also assumed that 10-20% of patients with plts > 50,000 that receive Len may not need Eltrombopag at all as there plts will not fall below 50,000.

Furthermore, since we will accrue patients with both high and low platelet counts, it is possible that the response rates to Lenalidomide will be different in these groups. These will be analyzed by exploratory studies.

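### Read literally, Section 11 limits the cytogenetic response rate to patients with an adequate post-treatment karyotype, which overstates the rate if the patients lost respond less often

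*Combined protocol and SAP*

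**What the plan says.** Section 4.1.2 lists as a secondary objective: "To evaluate the frequency of bone marrow response (CR+PR) and cytogenetic response". It gives no threshold, test or denominator.

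The cytogenetic paragraph of Section 11 opens with a laboratory standard: "Requires 20 analyzable metaphases when using conventional techniques". It then adds: "Analysis of data will require 20 metaphases before and after treatment". FISH may supplement the karyotype, but "it is not a substitute for conventional cytogenetic studies". Complete response is defined as "Restoration of a normal karyotype in patients with a documented pre-existing clonal" chromosome abnormality, so the endpoint applies only to patients who are abnormal at baseline.

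Other relevant text:
- Section 2 (schedule) and Sections 5.1 and 6.3 call for a marrow during treatment and again when treatment or study participation ends. Section 8.4 follows early discontinuers for response.
- Section 8.3 lists the reasons for stopping. They include withdrawn consent, loss to follow-up, adverse events, lack of effect and progression.
- The general response list in Section 11 counts death on treatment as a failure. The cytogenetic paragraph does not repeat this.
- Section 14.1 defines a safety population only. Section 5.1 refers to 52 evaluable subjects without defining the term.
- Section 14.2 bases the stopping and success rules on another endpoint: "The primary outcome is major erythroid response".

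**The concern.** The baseline half of the requirement is sound: a patient with a normal or failed baseline karyotype cannot show a cytogenetic response, and Section 6.1 does admit some patients with failed baseline cytogenetics. The post-treatment half is different, because it selects patients on something that happens after treatment starts. A patient who dies, withdraws consent or disappears before a second marrow, or whose second sample yields too few metaphases, would leave the analysis rather than count as not having responded.

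Some of those reasons are likely to go with poor outcome. If so, the rate among patients with both samples is higher than the rate among all patients who could have responded. The group abnormal at baseline is only part of a maximum of 52 patients, so a few exclusions can move the percentage visibly. With no denominator written down, the choice could also be made after the results are known.

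**Working it through.** The plan states no cytogenetic response rate, denominator or missing-marrow rate, so there is no figure to reproduce. The check is how far the two denominators can diverge.

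**Notation.** M = treated patients with a clonal abnormality on an adequate baseline karyotype; R = responders with both samples; m = patients among the M without an adequate post-treatment karyotype; f = m/M; q = the response rate the missing patients would have shown.

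- Rate in patients with both samples: r = R/(M − m).
- Rate in all M patients: r(1 − f) + qf.
- Overstatement: r − [r(1 − f) + qf] = f(r − q).

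The overstatement is zero if q = r, and largest, at f × r, if q = 0.

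**Inputs.** For r I take 65%, only as a plausible reported value. It is the figure in Section 3.4 for an earlier lenalidomide study: "Eleven of 17 (65%) patients with karyotypic abnormalities had a 50% or greater reduction in abnormal metaphases". The values of f (5%, 10%, 20%) and q are assumptions.

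| f | q = 0 | q = 32.5% (half of r) | q = 65% |
|---|---|---|---|
| 5% | 0.65 × 0.95 = 61.75% | 61.75% + 1.625% = 63.4% | 65% |
| 10% | 0.65 × 0.90 = 58.5% | 58.5% + 3.25% = 61.75% | 65% |
| 20% | 0.65 × 0.80 = 52.0% | 52.0% + 6.5% = 58.5% | 65% |

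With q = 0 the overstatement is 3.25, 6.5 and 13 points. With q at half of r it is half as much. With q = r there is none.

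**In whole patients.** Assume M = 20 and R = 10, with no responders among the missing. All 20 in the denominator gives 10/20 = 50.0%. Dropping two gives 10/18 = 55.6%, and dropping four gives 10/16 = 62.5%.

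**Against sampling error.** With about 20 patients (again an assumption), the standard error at 65% is √(0.65 × 0.35/20) = 10.7 points. The largest overstatement at 5% or 10% missing is below one standard error; at 20% missing it is above. Unlike sampling error, this bias does not appear in the confidence interval.

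**The case against.** The strongest reply is that the sentence is a laboratory standard. It sits among the response definitions, next to the metaphase count and the FISH limit. Read that way, a patient without 20 post-treatment metaphases cannot be called a responder but stays in a baseline-defined denominator, and nothing is inflated. This stands to the extent that exclusion is a reading of the text and is nowhere stated outright. It does not settle the matter: the preceding sentence already sets the laboratory standard, the second sentence speaks of analysis, and on either reading no denominator is given.

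The second reply also stands in part. Because a marrow is due at discontinuation, stopping treatment does not by itself remove a patient. The loss is confined to deaths, withdrawn consent, loss to follow-up and failed samples.

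Four stronger readings are tempting, and the documents do not support them.

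- *That the rate is overstated as a matter of fact.* The direction depends on why samples are missing. Failures unrelated to response cause no bias.
- *That the earlier study sizes the problem, with 17/43 abnormal at baseline and 7/43 lost.* Section 3.4 says: "Among the 36 patients completing more than one cycle of treatment, 24 (67%) experienced an erythroid response". Its response rates by karyotype among evaluable patients (91%, 68%, 17%), with 24 responders in 36, fit only 10/11, 13/19 and 1/6. The abnormal karyotypes are then 11 + 6 = 17 of the 36, so 43 appears to be the wrong base. The remaining 43 − 36 = 7 patients did not complete more than one cycle, which is not a missing-marrow rate; here such patients are due a discontinuation marrow.
- *That the rate becomes non-comparable with the 70% intent-to-treat figure in Section 3.4.* No such comparison is planned, and that figure comes from a trial restricted to del(5q) patients, so a mixed-karyotype group would differ from it anyway.
- *That the same defect affects CR+PR.* The sentence belongs to the cytogenetic paragraph and does not govern marrow response.

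**Conclusion.** The point holds in a limited form. The literal text produces a both-samples rate, and nothing elsewhere says how patients without an adequate second karyotype are counted. Around a reported 65%, the overstatement runs from zero (missingness unrelated to response) to 3.25, 6.5 or 13 points at 5%, 10% or 20% missing (no missing patient responds). The missing fractions and the response rate among missing patients are assumptions, because the documents give neither.

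The effect is confined to a secondary, descriptive frequency. The go/no-go decision is untouched. It is still worth correcting, because the correction is cheap and removes a choice that could otherwise be made after seeing the data.

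**What to change.** Keep 20 analyzable metaphases as the requirement for calling a cytogenetic response. Replace the sentence on data analysis with wording such as:

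> The denominator for cytogenetic response is all treated patients with a documented clonal abnormality on an adequate baseline karyotype (20 analyzable metaphases). A patient without an adequate post-treatment karyotype, for any reason, counts as a non-responder. The number of such patients and the reasons will be reported. The rate in patients with adequate karyotypes at both times is a supporting analysis.

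An exact confidence interval should accompany the rate.

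The change needs no extra patients, visits or samples. The reported rate will be somewhat less favourable, and it is conservative where a sample fails for purely technical reasons. The supporting analysis and the listed reasons let the reader see how much of the difference comes from that.

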Appendix 2: ECOG Performance Status Scale

Appendix 3: Cockcroft-Gault estimation of CrCL

Appendix 4: International Prognostic Scoring System (IPSS) for MDS

Appendix 5: NCI CTC Version 4.0

Appendix 6: Correlative Studies

1 PROTOCOL SYNOPSIS

PROTOCOL TITLE:PHASE II STUDY OF LENALIDOMIDE AND ELTROMBOPAG IN PATIENTS WITH SYMPTOMATIC ANEMIA IN LOW OR INTERMEDIATE I MYELODYSPLASTIC SYNDROME (MDS)	
DATE PROTOCOL FINAL:	08 JULY 2011
INDICATION:	MDS
STUDY PHASE:	Phase II

BACKGROUND AND RATIONALE:The rationale for this study is that combined treatment with eltrombopag (PROMACTA) and lenalidomide (REVLIMID) will reduce the incidence of lenalidomide induced thrombocytopenia thus enabling patients to tolerate the required duration of lenalidomide therapy leading to higher rates of response to lenalidomide. A major reason why lenalidomide cannot be used for the treatment of MDS is because of the occurrence of thrombocytopenia. The use of eltrombopag will potentially raise platelet counts in these patients and enable a longer exposure to lenalidomide. Secondly, thrombocytopenia in the first 2 months after lenalidomide therapy predicts the subsequent response to lenalidomide treatment in patients with low risk MDS. Thus raising platelet counts to enable continuation of Lenalidomide therapy is important in these patients. Lastly, an increase in blasts has been a potential concern with the use of thrombopoietin mimetics. Preclinical studies have indicated that eltrombopag is less likely to increase blasts thus making it a possible potential therapeutic candidate in low risk MDS.
	

STUDY OBJECTIVES:
 
Primary Objectives:
 
To evaluate the rate of hematologic improvement of the eltrombopag/lenalidomide combination as defined by the IWG 2006 criteria
 
To evaluate the safety and tolerability of the eltrombopag/lenalidomide combination in patients with low –intermediate risk MDS
 
Secondary Objectives
 
To compare the time to hematologic improvement
 
To evaluate the duration of hematologic improvement
 
To evaluate the effect of combination treatment on platelet counts, platelet transfusions and bleeding events.
 
To evaluate the frequency of bone marrow response (CR+PR) and cytogenetic response.
 
To evaluate the relationship between mutations in bone marrow stem cells and response
 
To evaluate the relationship between various stem and progenitor alterations and response
	

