6.1 Inclusion Criteria

Subjects must meet the following inclusion/exclusion criteria to be eligible for the study.

- 1 Age \geq 18 years.
2. Patient must have a documented diagnosis of MDS according to World Health Organization (WHO) criteria (see Appendix IV) or non-proliferative chronic myelomonocytic leukemia (CMML) (WBC \leq 12,000/uL).
3. Patients must have International Prognostic Scoring System (IPSS) categories of Low- or Intermediate-1-risk disease (see Appendix 4).
4. Patients must have symptomatic anemia untransfused with hemoglobin \leq 10.0g/dL within 8 weeks of registration or with RBC transfusion-dependence (i.e., \geq 2 units/month) confirmed for a minimum of 8 weeks before randomization. Or patients have platelet $<$ 50,000/uL with hemoglobin $>$ 10.0 g/dL.
5. Patients must have IPSS score determined by cytogenetic analysis prior to randomization. Patients with cytogenetic failure and \leq 10% marrow blasts will be eligible.
6. Patients must be off all disease modifying therapy for MDS for 28 days prior to initiation of study treatment. Patients may receive hydrocortisone prophylactically to prevent transfusion reactions.
7. Patients must not have documented iron deficiency. All patients must have documented marrow iron stores. If marrow iron stain is not available, the transferrin saturation must be \geq 20% or a serum ferritin \geq 100 ng/100 mL or soluble transferrin receptor $<$ 5mg/L.
8. Women must not be pregnant or breastfeeding. Females of childbearing potential should have 2 negative pregnancy tests (sensitivity of at least 50 mIU/mL). The

first test should be performed within 10-14 days, and the second test within 24 hours prior to prescribing lenalidomide.

9. Females of reproductive potential must adhere to the scheduled pregnancy testing as required in the Revlimid REMS® program. Able to take aspirin (81 or 325 mg) daily as prophylactic anticoagulation (patients intolerant to ASA may use warfarin or low molecular weight heparin).

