8.2 SUPPORTIVE CARE

1. All supportive measures consistent with optimal patient care will be given throughout the study.

2. Therapies considered necessary for the patient's well being may be administered at the discretion of the Investigator. These therapies include antibiotics, analgesics, antihistamines, or other medications, and transfusions of red blood cells, platelets, or fresh frozen plasma given to assist in the management of complications associated with MDS or study treatment.

3. Packed RBCs: Transfusions of two units of packed RBCs should be considered for decline in hematocrit (HCT) to $< 25\%$ or symptoms of cardiovascular compromise. The following **transfusion thresholds and guidelines** are recommended for study participants: HCT $< 25\%$, two units of packed RBCs; HCT $< 21\%$, three units of packed RBCs; HCT $< 18\%$, four units of packed RBCs.

4 Platelets: Eight to ten units of random donor platelets or one cytopheresis unit of single donor platelets should be administered to all subjects with signs of hemostatic failure (i.e., bleeding or petechiae) or life threatening thrombocytopenia (i.e., platelet count $< 10,000/\mu\text{L}$).

5 Patients should not receive androgens or steroids for supportive treatment of their anemia or thrombocytopenia

6 Patients may receive hydrocortisone prophylactically to prevent transfusion reactions. Steroids given for adrenal failure, hormones administered for non-cancer related conditions (e.g. insulin for diabetes), and intermittent uses of dexamethasone as an antiemetic are permitted concomitantly with study drug. Short courses of steroids to treat study drug-induced skin rashes are also permitted.

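### The erythroid response rule has no erythropoietin condition, although Section 11 sets one for CR and the protocol does not bar the drug on study

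*Combined protocol and SAP*

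**What the plan says.** **Response rules (Section 11).** For complete remission, the hemoglobin criterion is "Hemoglobin greater than 11 g/dL (untransfused, patient not on erythropoietin". The neutrophil and platelet criteria carry parallel conditions on growth factors and thrombopoietic agents. For hematologic improvement, the erythroid rule has two limbs: "Hgb increase by 1.5 g/dL if not transfusion dependent", or at least 4 fewer RBC transfusions per 8 weeks. Improvement must last more than 8 consecutive weeks. Neither limb mentions erythropoietin.

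**Primary outcome.** The synopsis objective is "To evaluate the rate of hematologic improvement of the eltrombopag/lenalidomide combination as defined by the IWG 2006 criteria". Section 14.2 instead states: "The primary outcome is major erythroid response". Section 11 does not define that term. The only description is in the background (Section 3.4), for an earlier lenalidomide study: "MER defined by sustained transfusion-independence (> 8 weeks) or a rise in hemoglobin >2 g/dl". It has no erythropoietin condition either.

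**On-study therapy.** Section 8.2 states: "Therapies considered necessary for the patient's well being may be administered at the discretion of the Investigator". Its one bar on anemia treatment is: "Patients should not receive androgens or steroids for supportive treatment of their anemia or thrombocytopenia". The prohibited list in Section 8.5 covers other TPO-R agonists, deferasirox, antiplatelet drugs and anticoagulants.

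**Washout.** Inclusion criterion 6 reads: "Patients must be off all disease modifying therapy for MDS for 28 days prior to initiation of study treatment". It does not name erythropoietin or govern use after entry.

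**The concern.** Section 11 recognizes, for CR, that supportive agents can distort blood counts. It does not carry that condition into hematologic improvement, which is the stated primary efficacy endpoint. Eligibility does not require failure of erythropoietin, and although serum erythropoietin is measured at screening, no cutoff applies. Patients who could respond to erythropoietin can therefore enroll, receive it under Section 8.2, and be scored as responders to the study regimen.

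There is no control arm to absorb this. Each such patient adds directly to the counts compared with 7 of 25 and 17 of 52.

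**Working it through.** **1. What the text lets through**

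| Point | CR hemoglobin | Erythroid response, hemoglobin limb | Erythroid response, transfusion limb |
|---|---|---|---|
| Erythropoietin excluded | Yes | No | No |
| Transfusion excluded | Yes | Only transfusion dependence | Not applicable |

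Example under Section 11: hemoglobin 8.8 g/dL at baseline, erythropoietin started in cycle 1, then 10.4 g/dL for more than 8 weeks. The rise is 10.4 − 8.8 = 1.6 g/dL, so the rule scores a response. Under the Section 3.4 description (rise above 2 g/dL), 1.6 would not qualify, but a larger erythropoietin-driven rise, or transfusion independence reached on erythropoietin, would.

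Dependence is set at 2 or more units per month at entry (Section 6.1, item 4) and at more than 2 units over 8 weeks in the relapse rule after CR or PR (Section 11). Transfusion below those levels is not excluded from the hemoglobin comparison.

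**2. Reproducing the stated design**

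Inputs from Section 14.2: null rate 25%, target 40%, n1 = 25, N = 52, success at 17 or more, false acceptance at most 10%, power 80%, expected N 32.4.

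With c the smallest stage 1 count that lets the trial continue:

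P(accept | p) = Σ over x from c to 25 of P(Bin(25, p) = x) × P(Bin(27, p) ≥ 17 − x)

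E(N | p) = 25 + 27 × P(Bin(25, p) ≥ c)

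| Stage 1 rule | Accept at 25% | Accept at 40% | Expected N at 25% |
|---|---|---|---|
| Stop at 7 or fewer (c = 8) | 0.0992 | 0.8003 | 32.38 |
| Stop at fewer than 7, as printed (c = 7) | 0.1179 | 0.8556 | 36.85 |

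The first row reproduces the stated properties and the printed boundary does not. That is a separate defect, so both rows are carried forward.

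**3. Illustrating the leak**

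Let q be the share of true non-responders scored as responders because of erythropoietin or transfusion. The documents give no value for q; the values below are assumptions. With a true rate of 25%, the scored rate is 0.25 + 0.75 × q.

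| q (assumed) | Scored rate | False acceptance, stop at ≤7 | False acceptance, printed rule |
|---|---|---|---|
| 0 | 25.0% | 9.9% | 11.8% |
| 2% | 26.5% | 14.8% | 17.5% |
| 5% | 28.75% | 24.3% | 28.3% |
| 10% | 32.5% | 44.1% | 49.9% |

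At q = 2%, the expected number of misclassified patients in a full trial is 52 × 0.75 × 0.02 = 0.78, fewer than one.

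**The case against.** **Silence is not permission.** The Concomitant MDS Therapy paragraph in Section 8.5 allows only G-CSF, Section 5.1 expressly permits only myeloid growth factors, and the washout might be read to include erythropoietin. How often erythropoietin would be used is conjecture. This stands against any claim that use will be common. It does not close the gap: no sentence bars the drug, and Section 8.2 gives broad discretion.

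**The IWG criteria are cited.** They are, but Section 11 writes out its own rules, with the qualifier for CR and without it for erythroid response. Sites will score from that text.

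**The 1.5 g/dL rule may not be what the boundaries count.** This stands. Section 14.2 counts major erythroid response, which Section 11 leaves undefined. The correction must therefore reach that definition too.

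**The benchmark may share the gap.** The 25% null cites an earlier lenalidomide study, and the documents do not show how its responses were scored. Tightening only this trial's rule could make the comparison less like-for-like. This stands as a limitation.

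**Transfusion as an equal route.** A reader might infer that a patient kept up by transfusion would routinely score on the hemoglobin limb. The text does not support this. A patient entering at 7.5 g/dL must hold 9.0 or more for over 8 weeks, while the Section 8.2 guideline transfuses at hematocrit below 25%, about 8.3 g/dL on the usual factor of three (an assumption). Each fall to that level breaks the run. Transfusion dependence also counts as relapse after erythroid improvement. Only occasional transfusion below the dependence level remains open.

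**Conclusion.** The omission is confirmed for erythropoietin in both limbs, and in a narrower form for occasional transfusion in the hemoglobin limb. It affects the primary outcome under either name, though which hemoglobin threshold applies depends on a definition the protocol does not supply.

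The size is unknown. The illustration shows sensitivity only: at a true rate of 25%, misclassifying 2% of non-responders takes false acceptance from 9.9% to 14.8%, or from 11.8% to 17.5% under the printed boundary. The 11.8% starting point comes from the boundary defect, not from this gap.

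A reader might combine high erythropoietin use with a high response to it and infer that false acceptance would exceed one half. The documents give neither rate, so no such figure can be attributed to this trial.

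This should be fixed before responses are scored for the 25-patient decision, since a later choice would be post hoc. It is an unguarded route to bias, not evidence that the planned analysis will fail.

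**What to change.** In Section 11, and in whatever definition Section 14.2 adopts for major erythroid response, state:

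- A patient who starts or increases erythropoietin after study entry, before completing the qualifying window of more than 8 weeks, counts as a non-responder and stays in the denominator. This applies to both limbs.
- A patient on unchanged erythropoietin since before entry remains assessable and is reported separately. A sensitivity analysis counts these patients as non-responders.
- For the hemoglobin limb, only values not influenced by RBC transfusion within the window count.

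This changes scoring only. Permitted care and N = 52 stay as they are. Concomitant drugs with doses and dates (Section 8.5) and RBC transfusion history (Section 2) are already recorded.

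The cost is that a true study-drug response in a patient who starts or increases erythropoietin is not counted, so the observed rate may be somewhat lower.

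Making every erythropoietin user a non-responder would be too blunt. If 10% to 30% of patients used it (an assumption) and none could score, a true 40% rate would be observed as 0.40 × 0.90 = 36% down to 0.40 × 0.70 = 28%. Power would fall from 85.6% to between 69.4% and 24.4% under the printed rule, or from 80.0% to between 62.9% and 20.9% with stopping at 7 or fewer. Limiting the rule to new or increased use targets the bias with less loss.
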